## **APPENDIX 2 THE ALGORITHM OF DERIVING THE TG ASSESSMENT BY GRANULAR SCORE AND STANDARD SCORE**

### A. By Standard Score

Q6 on Final EAC Biopsy Assessment Form (New or worsening TG)		TG Assessment at Month 6 (Standard Score)
YES = Failure (Having new or worsening TG)		NO = No Failure
NO		NO
YES		YES
INSUFFICIENT DATA		YES

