### **4.5 Per-protocol Analysis Set-1 (PPS1)**

The Per-protocol Analysis Set-1 will consist of all subjects in the FAS who have taken at least 5 of the 7 planned doses, are assessed for TG at 6 months after initiation of treatment or have post-baseline biopsy-proven new or worsening TG within 6 months of initiation of treatment, and do not have predefined major protocol deviations that may affect the primary efficacy endpoint.

These protocol deviations will be identified prior to unblinding of the study.

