### 10.1 Primary Efficacy Endpoint(s) and Analysis

The primary efficacy endpoint is defined as the proportion of subjects with new or worsening TG at 6 months post-treatment as adjudicated by the pathology EAC based on 2013 Banff criteria (standard score). New or worsening TG at 6 months by the standard score is defined as an increase of 1 or more between qualifying biopsy and 6-month biopsy. Subjects who do not have the TG assessment at 6 months post-dose will be assigned as failures, i.e. having ‘new or worsening TG’.

The primary analysis specified below will be performed based on the FAS for the first and second interim analysis of this study. As a sensitivity analysis, the primary analysis will be also performed based on Per-protocol Analysis Set-1 in the second interim analysis of the study.

The primary endpoint will be presented as the proportion of subjects with new or worsening TG determined at 6 months, and their difference between treatments (  $\Delta_{Cinryze-Placebo}$  ) is defined as follows:

$$\Delta_{Cinryze-Placebo} = \Pi_{Cinryze} - \Pi_{Placebo}$$

where  $\Pi_{Cinryze}$  is the proportion of new or worsening TG at 6 months post treatment in the CINRYZE group and  $\Pi_{Placebo}$  is the proportion of new or worsening TG at 6 months post treatment in the placebo group.

The analysis will employ a type I error rate of 0.025 to test null hypothesis:

$$H_0 : \Pi_{Cinryze} - \Pi_{Placebo} \geq 0$$

Against the 1-sided alternative:

$$H_a : \Pi_{Cinryze} - \Pi_{Placebo} < 0$$

There will be two interim analyses to assess the primary endpoint.

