where  $Z_1$  is the normalized test statistic at first interim stage, and  $Z_2$  is the normalized test statistic for incremental sample size  $n_2^*$  for second interim stage after the sample size adjustment. If the number of TG events exceeds 5 for all four cells in the contingency table of treatment versus TG event,  $Z_i$  ( $i = 1, 2$ ) will be obtained using normal approximation, otherwise  $Z_i$  ( $i = 1, 2$ ) will be calculated from p-value of Fisher's Exact test as (Lechmacher et al., 1999):

$$Z_i = \Phi^{-1}(1 - p_i)$$

where  $\Phi^{-1}(.)$  is the function to return a quantile from the standard normal distribution,  $p_1$  is the p-value from Fisher's Exact test for the first interim stage, and  $p_2$  is the p-value from Fisher's Exact test for incremental sample size  $n_2^*$  for second interim stage after the sample size adjustment.

If  $Z_{CHW} \geq Z_{1-\alpha/2, 49}$  (equivalent to the p-value from the test  $\leq 0.0249$ ), the null hypothesis will be rejected. Otherwise, the futility of the study will be claimed.

The following sensitivity analyses will be conducted for TG assessment by the granular score for the FAS and then TG assessment by the standard score and the granular score for Per-Protocol Analysis Set-1:

- Sensitivity analysis 1: Primary analysis will be repeated based on Month 6 TG assessment by granular score for the Full Analysis Set
- Sensitivity analysis 2: Primary analysis will be repeated based on Month 6 TG assessment by standard score for the Per Protocol Analysis Set-1
- Sensitivity analysis 3: Primary analysis will be repeated based on Month 6 TG assessment by granular score for the Per Protocol Analysis Set-1

The TG assessment by the granular score at 6 months is defined as the following:

- Worsening TG is defined as an increase of 6.25 in the glomerular capillary double contour percentage between qualifying biopsy and 6-month biopsy.

- New TG is defined by granular Banff (based on 2013 Banff criteria) cg 0 score in the qualifying biopsy and granular Banff (based on 2013 Banff criteria) cg score of greater than 0 in the 6-month biopsy.

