In order to demonstrate the stability of the primary analysis method, sensitivity analyses will be performed at the point of final analysis of primary endpoint (i.e. second interim analysis for study) by using multiple imputation (MI) assuming missing at random (MAR) to assign missing endpoint and/or combined with Cochran–Mantel–Haenszel (CMH) test for treatment effect. The CMH model will assess the treatment effect controlling for (1) donor characteristic (living vs deceased), (2) baseline AMR severity (severe vs mild to moderate) and possibly (3) time to onset of qualifying AMR from current transplant (>100 days vs  $\leq$ 100 days) if degree of freedom allows. Sensitivity analyses defined below will be based on the FAS.

	Statistical Test	Logic to assign the missing TG assessment at 6 months
Primary analysis model	Fisher's Exact with CHW weighted test	If no TG assessment at 6 months, assign as failure.
Sensitivity analysis 4	Fisher's Exact with CHW weighted test	If no TG assessment at 6 months, perform MI.
Sensitivity analysis 5	CMH with CHW weighted test	If no TG assessment at 6 months, assign as failure.
Sensitivity analysis 6	CMH with CHW weighted test	If no TG assessment at 6 months, perform MI

For multiple imputation, a monotone missing pattern will be assumed and logistic regression model will be utilized. The imputation seed will be 83789524 and number of imputations will be set as 100. The logistic regression model may contain the following factors (descending order by importance) to impute the missing TG assessment at 6 months:

- (1) Treatment group (CINRYZE vs placebo);
- (2) AMR severity at baseline (severe vs mild/ moderate);
- (3) Donor characteristics (living donor vs deceased donor);
- (4) Normalized eGFR change ( $\Delta_{eGFR}$ ).  $\Delta_{eGFR} = \frac{eGFR_{baseline} - eGFR_{last}}{T}$ , where   
 $eGFR_{baseline}$  is the last eGFR results prior to the first dose of investigational product,  $eGFR_{last}$  is the last eGFR result before or at Month 6 or early discontinuation visit, and T = (last eGFR assessment date – Date of first dose + 1)/30.25;
- (5) Resolution of qualifying AMR (Resolved by 6 months /early discontinuation vs unresolved by 6 months/early discontinuation);

(6) AMR free time in months, which defines as (date of Month 6 or early discontinuation visit – Date of first dose +1 – number of days with AMR)/30.25

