For sensitivity analysis 4, multiple imputation will be used to impute the primary endpoint for subjects without TG assessment at 6 months. The p-values from Fisher's Exact tests will be computed for each imputed dataset and transformed to  $\chi^2$ -distribution with degree of freedom (df) = 2 using Fisher's transformation ([Fisher, 1932](#)):

$$\Psi_i^{(m)} = -2 \log(p_i^{(m)}) \sim \chi_2^2 \quad (\text{Formulae 2})$$

where  $p_i^{(m)}$  is the p-value from Fisher's Exact test and  $\Psi_i^{(m)}$  is the transformed  $\chi^2$ -distribution for the  $i$ -th interim stage ( $i = 1, 2$ ) of the  $m$ -th ( $m = 1, 2, \dots, 100$ ) imputed dataset.

Then, Wilson-Helferty transformation ([Wilson & Helferty, 1931](#); [Goria, 1992](#)) will be used to transform the  $\chi^2$ -distribution to an asymptotic normal distribution with mean 0 and variance 1, as following:

$$Z_{WH,i}^{(m)} = \frac{\left(\frac{\Psi_i^{(m)}}{df}\right)^{1/3} - \left(1 - \frac{2}{9 \times df}\right)}{\left(\frac{2}{9 \times df}\right)^{1/2}} \quad (\text{Formulae 3})$$

where  $\Psi_i^{(m)}$  is the  $\chi^2$ -distributed statistic from the  $m$ -th imputed dataset,  $df$  is the number of degrees of freedom associated with  $\Psi_i^{(m)}$ , and  $Z_{WH,i}^{(m)}$  is the transformed value.

The transformed normal statistics  $Z_{WH,i}^{(m)}$  will be combined using multiple imputation analysis for the first interim stage and the second interim stage, respectively. Then the combined statistics  $Z_{WH,1}$  and  $Z_{WH,2}$  will be used to calculate the CHW weighted test statistic  $Z_{CHW}$  as:

$$Z_{CHW} = \sqrt{\frac{15}{30}} Z_{WH,1} + \sqrt{\frac{15}{30}} Z_{WH,2} \quad (\text{Formulae 4})$$

For sensitivity analysis 5, the same approach for handling missing data as for the primary analysis will be considered. CMH test will be performed to evaluate the treatment effect with controlling for baseline AMR severity and donor characteristic. The p-values from CMH general association statistics for the first and second interim stages will be used to yield the CHW weighted test statistic  $Z_{CHW}$  as formulae 1.

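### SAP Appendix 2 codes an EAC reading of insufficient data as new or worsening TG for every analysis set, and the SAP never says whether such a reading counts as a Month 6 TG assessment

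*SAP*

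**What the plan says.** - **Coding.** In Appendix 2, A. By Standard Score, the adjudicated answer on new or worsening TG can be NO, YES or "INSUFFICIENT DATA". The third answer gives a Month 6 TG assessment of YES, and the table defines YES as failure, that is, having new or worsening TG. Appendix 2, B. By Granular Score appears to do the same when both of its questions return insufficient data; its columns print irregularly, so the point rests mainly on part A. Neither part limits the rule to an analysis set.
- **Primary rule.** SAP 10.1: "Subjects who do not have the TG assessment at 6 months post-dose will be assigned as failures".
- **Per-protocol Set-1 (PPS1).** SAP 4.5 admits FAS subjects with at least 5 of 7 doses and no relevant major deviation who "are assessed for TG at 6 months after initiation of treatment or have post-baseline biopsy-proven new or worsening TG within 6 months" of starting treatment.
- **Per-protocol analyses.** Sensitivity analysis 2 in SAP 10.1: "Primary analysis will be repeated based on Month 6 TG assessment by standard score for the Per Protocol Analysis Set-1". Analysis 3 is the granular counterpart.
- **Imputation.** The SAP 10.1 table gives the rule for analyses 4 and 6 as "If no TG assessment at 6 months, perform MI". The text on analysis 4 says "multiple imputation will be used to impute the primary endpoint for subjects without TG assessment at 6 months". The text on analysis 6 is wider: it covers subjects with no post-dose TG assessment and also early discontinuers who had one when they left.
- **What is still produced.** After the futility decision (SAP 17), the SAP 20 list keeps the PPS1 TG summaries, Tables 14.2.1.1c and d. It drops the imputation tables (14.2.1.2 and 14.2.1.4) and the PPS1 Fisher table (14.2.1.5).

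**The concern.** Counting an unknown TG outcome as a failure is the declared primary rule in the FAS, and for that analysis the Appendix 2 coding agrees with it. The per-protocol and imputation analyses serve another purpose: they show whether the result depends on that rule. If the derived variable already holds YES for a biopsy that could not be read, the unknown outcome reaches those analyses as an observed event. They then repeat the assumption they are meant to test. The live consequence is in Tables 14.2.1.1c and d, where unreadable tissue could be reported as adjudicated new or worsening TG.

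**Working it through.** **1. Is Appendix 2 only the primary missing = failure rule?** Three features of the text suggest that its reach is wider.
- Part B derives the granular score. SAP 10.1 uses that score only in sensitivity analyses 1 (FAS) and 3 (PPS1), never in the primary analysis.
- The derived variable carries the same name as the quantity that analyses 2 and 3 and Tables 14.2.1.1c and d summarise.
- Part A codes an adjudication reading and has no row for a biopsy that was not done. SAP 10.1 covers the absent assessment in separate text.

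**2. Consequences if applied as written.** The variable is filled, so an imputation procedure that replaces only missing values leaves it alone. This holds for analysis 4, and for analysis 6 among subjects who reached Month 6. In PPS1 the subject counts as an event if an insufficient-data reading qualifies as being assessed for TG. SAP 4.5 does not settle that.

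**3. The plan's own figure.** Inputs from SAP 2.5: TG in 50% on placebo and 10% on CINRYZE, 30 per arm, one-sided 0.025, at least 90% power. A single one-sided Fisher test at 30 per arm has exact power 91.4%, so the stated figure reproduces. For the planned combination in SAP 10.1 (two stages of 15 per arm, Fisher p-value per stage, equal CHW weights, level 0.0249), exact enumeration gives 85.1%. That is the baseline below.

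**4. Effect of the coding.** Let q be the share of unreadable biopsies, independent of true TG status. The documents give no value; 5 to 20%, equal in both arms, is an assumption. Coded as events, a rate p becomes p + (1 − p)q, so the difference becomes 40(1 − q) points. For q = 10%: 0.50 + 0.50 × 0.10 = 0.55 and 0.10 + 0.90 × 0.10 = 0.19.

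| q | Placebo v CINRYZE | Difference (points) | Power, coded as TG | Power, left out (per arm, by stage) |
|---|---|---|---|---|
| 0 | 50% v 10% | 40 | 85.1% | 85.1% (15 + 15) |
| 5% | 52.5% v 14.5% | 38 | 76.3% | 82.1% (14 + 14) |
| 10% | 55% v 19% | 36 | 67.6% | 79.9% (14 + 13) |
| 20% | 60% v 28% | 32 | 52.2% | 71.2% (12 + 12) |

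Leaving the subjects out keeps 50% v 10% but costs sample size. At q = 20% the total loss is 85.1 − 52.2 = 32.9 points. Of these, 85.1 − 71.2 = 13.9 would be lost anyway and 71.2 − 52.2 = 19.0 come from the coding. At 5% and 10% the coding accounts for 82.1 − 76.3 = 5.8 and 79.9 − 67.6 = 12.3 points.

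**5. Unequal shares.** With 5% unreadable on placebo and 15% on CINRYZE, the rates are 52.5% v 23.5%, a difference of 29 points. With 15% and 5%, they are 57.5% v 14.5%, a difference of 43 points. The direction is not fixed.

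**The case against.** The strongest reply is that Appendix 2 merely programs the missing = failure rule, and that the SAP's other definitions already handle these subjects. An insufficient reading is arguably not an assessment of TG, and it is certainly not biopsy-proven TG, so SAP 4.5 can be read to exclude the subject from PPS1. On the same view it is an absent assessment for analyses 4 and 6. The Appendix 1 sample code imputes a response variable without saying whether that variable has already been failure-coded. Nor do the documents show how the adjudication form records a biopsy that was never done, so a clean contrast between unreadable and missed biopsies cannot be drawn.

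This stands in part. A reader might infer that unreadable biopsies certainly remain events in PPS1 and are never imputed. The documents do not support that: both are consequences of applying Appendix 2 literally where other text is silent. The reply does not remove the problem, because the one rule that is written down is unconditional and is also written for a score used only in sensitivity analyses. Two programmers could produce different PPS1 tables.

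Other points for the plan also stand. The imputation tables are not produced, and the PPS1 tables kept are summaries without a test. Protocol 7.2.2.2 requires at least two cores containing cortex at Month 6, which should limit inadequate samples. Table 14.2.1.7 (biopsy data availability) and Listings 16.2.6.1.1 and 16.2.6.1.4 are kept and may let a reader find such cases, although Table 14.2.1.7 covers the FAS and not PPS1.

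**Conclusion.** The point holds as a conflict between an unconditional coding rule and the purpose of the analyses that would use it, made worse by a missing definition of assessed. The live effect is on Tables 14.2.1.1c and d. The effect on analyses 4 and 6 matters only if those are run.

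The size is illustrative. At an assumed equal share of 5 to 20%, the 40-point difference shrinks to between 38 and 32 points. Stage-wise power at 60 subjects falls to between 76.3% and 52.2%, against 82.1% to 71.2% if those subjects are left out. It would be wrong to attribute the whole power loss to the coding, and no retained PPS1 hypothesis test depends on these figures.

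A reader might also infer that the coding influenced the futility decision, since SAP 10 bases conditional power on the FAS and PPS1, and SAP 17 says that the committee's recommendation came from one sensitivity analysis. The SAP does not say which analysis that was or how many readings were insufficient, so no such effect can be claimed. The FAS primary result is unaffected.

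**What to change.** 1. In Appendix 2, parts A and B, map insufficient data to MISSING.
2. Apply missing = failure as a separate, labelled step, only in the FAS analyses that specify it: the primary analysis and sensitivity analyses 1 and 5.
3. State in SAP 4.5 that an insufficient-data reading is not a Month 6 TG assessment. Treat these subjects as not assessed in PPS1 and in Tables 14.2.1.1c and d, and as missing in analyses 4 and 6 if those are run.
4. In Tables 14.2.1.1a and b, show observed TG and failures assigned by rule on separate rows.

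The cost is a small change to the derivation (the same line in each algorithm), one sentence in SAP 4.5 and extra rows in two tables. The downside is a PPS1 smaller by the number of unreadable biopsies.

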### B. By Granular Score

Q3 on Final EAC Biopsy Assessment Form (Worsening TG)		Q4 on Final EAC Biopsy Assessment Form (New TG)	TG Assessment at Month 6 (Granular Score)
NO	NO	NO	NO
NO	NOT APPLICABLE	NO	NO
NO	YES	YES	YES
YES	NO	NO	YES
YES	NOT APPLICABLE	NO	YES
INSUFFICIENT DATA	INSUFFICIENT DATA	NO	YES
YES	YES	YES	YES
